5. ABBREVIATIONS AND DEFINITIONS OF TERMS

Abbreviation	Definition
ADME	Absorption, distribution, metabolism and excretion
AE	Adverse event
ALT	Alanine aminotransferase
ANCOVA	Analysis of covariance
ANOVA	Analysis of variance
AST	Aspartate aminotransferase
BMI	Body mass index
BUN	Blood urea nitrogen
°C	degrees Celsius
CGI-C	Clinician's Global Impression of Change
CGI-S	Clinician's Global Impression of Severity
CI	Confidence interval
cm	Centimeter
CNS	Central nervous system
E	number of events
ECG	Electrocardiogram
eCRF	Electronic report form
ePRO	Electronic patient reported outcomes
EOT	End of Treatment
FDA	Food and Drug Administration
FFD	Fingers to floor distance
g	gram
GCP	Good Clinical Practice
GGT	Gamma glutamyltransferase
HCl	Hydrochloride
IATA	International Air Transport Association
ICH	International Council for Harmonisation
IRB	Institutional Review Board
ITT	Intent-to-Treat
IUD	Intrauterine device
kg	Kilogram
kg/m ²	Kilogram per meter squared

Abbreviation	Definition
LC/MS/MS	Liquid chromatography with tandem mass spectrometric detection
LOCF	Last observation carried forward
LOQ	Limit of quantification
LSMD	Least squares mean difference
MedDRA	Medical Dictionary for Regulatory Activities
mg	Milligram
mL	Milliliter
mm	Millimeter
msec	Millisecond
N	Number
NRS	Numerical Rating Scale
NSAID	Nonsteroidal anti-inflammatory drug
PGI-C	Patient's Global Impression of Change
PGI-S	Patient's Global Impression of Severity
pH	Potential of hydrogen
PK	Pharmacokinetic(s)
PP	Per-Protocol
PT	Prothrombin time
QA	Quality assurance
QC	Quality control
SAE	Serious adverse event
SD	Standard deviation
SE	Standard error
SOPs	Standard operating procedures
TEAE	Treatment-emergent adverse event
TENS	Transcutaneous Electrical Nerve Stimulation
TID	Three times a day
TSH	Thyroid stimulating hormone
VAS	Visual Analogue Scale

6.2. Serious Adverse Event Reporting Contact Information - Sponsor

Serious adverse events (SAEs) should be reported to Precision within 24 hours via the EDC system after Investigator or Investigator’s representative becomes aware of their occurrence.

6.3. Central Laboratory

The central laboratory, ACM Global Central Laboratory ("ACM"), for serum chemistry, hematology and urinalysis will be used.

The genotype laboratory, Machaon Diagnostics, (Machaon), testing for CYP450 2D6 polymorphism will be used.

7. BACKGROUND AND RATIONALE FOR THE STUDY

7.1. Introduction

Tolperisone, a centrally acting muscle relaxant, is widely used in Europe, Asia, and South America for the treatment of abnormally increased muscle tone. Tolperisone is an (non-opioid) oral formulation presented as film-coated tablets, and is being developed by Neurana Pharmaceuticals, Inc. for the treatment of symptoms associated with acute and painful back muscle spasms.

The mechanism of action of tolperisone is not fully characterized. The most prominent effect of tolperisone is its inhibitory action on pathways of spinal reflexes. It suppresses the mono and polysynaptic reflex transmission by both pre-synaptic and post-synaptic mechanisms. Tolperisone has sodium (Na⁺) and, to a lesser extent, calcium (Ca²⁺) channel blocking activity. It inhibits, in a relatively selective manner, voltage-gated Na⁺ channels. However, even with high tolperisone concentrations, channel blockade remains incomplete and reversible. Although it demonstrated significant binding to a variety of receptors *in vitro*, including the sigma σ_1 receptor, the functional effects of tolperisone at these targets is not known. In general, tolperisone causes a frequency-dependent decrease in action potential amplitude of axonal membranes. Excitability is then decreased, especially in cases of pathologically increased reflex activity. It has been proposed that tolperisone may exert a stronger inhibitory effect on sensory axons than motor axons, as indicated by inhibition of nociception-induced reflex muscle contraction and withdrawal in animal models. Vasodilatory properties of tolperisone have been repeatedly described in clinical studies. The mechanism of the blood flow-enhancing effect of

tolperisone has not been investigated systematically; however, Ca²⁺-channel antagonism, or the drug's modest anti-alpha-adrenergic effects may be involved.

Animal toxicity has been extensively profiled and in repeat dosing study in rats with daily doses of 100 mg/kg for 28 days being well-tolerated, and the no observed adverse effect level (NOAEL) considered to be 300 mg/kg/day. No target organs of toxicity were identified. In a three-part, 28-day toxicology study in dogs, the NOAEL was established as 20 mg/kg/day. Chronic oral toxicity studies in the rat (6-month) and dog (9-month) have been reported and have shown NOAELs of 50 and 5 mg/kg/day, respectively.

Tolperisone was nonmutagenic in the Ames test and in two *in vivo* mouse bone marrow micronucleus tests. Tolperisone was, however, clastogenic in the *in vitro* chromosomal aberration assay in human lymphocytes and the *in vitro* mouse lymphoma TK assay. The *in vitro* genotoxic activity was attributed to 4-MMPPO, a degradation product of tolperisone. The ICH guidelines for genotoxic impurities require that levels remain below 10 ppm, equivalent to a daily maximum exposure of 1.5 ug. Based on daily dosing of 450 mg tolperisone, the calculated limit of 4-MMPPO is 3.3 ppm/tablet (corresponding to 1.5 µg per total daily dose). Carcinogenicity studies in rats and mice have shown no risk of carcinogenic potential. Tolperisone had no effect on fertility or in pre- and postnatal reproductive toxicity studies in rats and was non-teratogenic in rats and rabbits.

Pharmacokinetic, toxicokinetic, and absorption, distribution, metabolism, and excretion (ADME) studies with tolperisone show the drug is highly absorbed (> 80%), widely distributed to major organs including the CNS, and excreted primarily by the kidneys. *In vitro* studies have demonstrated that tolperisone is rapidly converted into as many as 25 metabolites by liver microsomes from rat, dog, and human species. *In vivo*, both major human metabolites M4 and M5 are present at high levels in dogs. M4 is also present at high levels in the rat, but M5 is not.

Tolperisone has been evaluated in five clinical studies conducted in healthy volunteers: two pharmacokinetic (PK) studies (Study 01-316-02 and Study 01-286-02); a safety and PK study (AV650-012), a drug-drug interaction study (AV650-019); and a study to assess sedative effects (Study 115). A total of 148 subjects were exposed to tolperisone in these studies. One double-blind, placebo-controlled safety and efficacy study was conducted in patients, Study AV650-018 (IND 74864) in patients with spasticity associated with multiple sclerosis (108 tolperisone during double-blind, 146 tolperisone during open-label).

The pharmacokinetic studies conducted with tolperisone in male and female healthy volunteers have demonstrated a roughly linear relationship between dose and exposure that is more than dose-proportional across the investigated dose range (between 150 to 450 mg administered orally in single doses). Additionally, gender has no apparent influence on tolperisone's pharmacokinetic behavior in human subjects. In contrast, the plasma exposure in rats was approximately twice as high in females as in males for a given dose. Food appears to increase the drug's plasma exposure slightly in humans.

Tolperisone is extensively metabolized *in vivo*, mainly by the liver enzymes CYP2D6 and CYP2C19. Moderate to potent inhibitors of CYP2D6 and CYP2C19 are thus likely to cause drug interactions with tolperisone. In a Phase 1 drug-drug interaction study, the tolperisone plasma exposure increased approximately 2 fold following concomitant administration with paroxetine (a CYP2D6 inhibitor) and increased by 3- to 4- fold following concomitant administration with

fluvoxamine (a CYP2C19 inhibitor). The CYP2D6 genotype (conferring ultra-fast, fast, intermediate and slow metabolizer phenotypes) influences tolperisone bioavailability. In one pharmacokinetic study, subjects who were classified as CYP2D6 intermediate metabolizers had approximately 50% higher exposure to tolperisone following oral dosing than fast metabolizers. Overall, the bioavailability increased with decreasing metabolic activity among the four genotypes.

In a driving simulation, Study 115, assessed the sedation risk tolperisone. Study 115 was a randomized, placebo-controlled, multiple-dose 3-way cross-over study of safety and cognitive effects of multiple doses of 150 mg tolperisone administered three times daily (*TID*) in 35 male and female healthy volunteers. Treatment groups included 450 mg tolperisone (150 mg *TID*), 30 mg cyclobenzaprine (i.e., 10 mg administered three times daily), and placebo. Subjects received 3 days of each treatment. In this study, tolperisone was equivalent to placebo at T_{max} , showed no drug accumulation or sedation effects following multiple doses, and showed no next day residual effects.

The most common AE across all studies was headache, occurring in 14.2% of subjects in healthy volunteer studies and 15.3% of subjects in patient studies. No other AEs occurred in more than 5% of subjects in either group of studies.

This Phase 2 study will explore the efficacy and safety of tolperisone at doses up to 600 mg administered *TID* for 14 days in patients with acute and painful back muscle spasms.

7.2. Drug Profile

[figure not shown]
Full details of tolperisone pre-clinical and clinical safety and tolerability data are contained in the Investigator's Brochure.

7.3. Rationale

7.3.1. Study Design

This is a double-blind, randomized, placebo-controlled, parallel group study of the efficacy and safety of tolperisone or placebo administered as multiple doses *TID* in approximately 400 male and female subjects experiencing back pain due to or associated with muscle spasm. The tolperisone groups consist of dose levels of 150, 300, 450, and 600 mg administered *TID* in doses of 50, 100, 150, or 200 mg for 14 days, with a visit at 28 days as follow-up. Subjects randomized to the placebo group will receive matching placebo tablets *TID* for 14 days with a follow-up visit at Day 28. Subject participation will be approximately 4 weeks.

The study design provides unbiased (through randomization) observations of the efficacy and safety of tolperisone over a range of doses (150 to 600 mg/day) administered for two weeks, as appropriate for acute back spasms and based on prior studies.

See the Schedule of Procedures in [Table 2](#).

7.3.2. Tolperisone Dose Levels

Tolperisone 50, 100, 150, and 200 mg tablets and matching placebo will be provided for the study by the Sponsor. Dosing will be three times a day/TID, with a single tablet administered at each dose for a total daily dose of 150, 300, 450, and 600 mg per day. Subjects should be instructed to dose at 6-8 am, 12-2 pm, and 6-8 pm daily for 14 days. Subjects who are experiencing significant pain following randomization will be allowed to take a single tablet of acetaminophen 500 mg up to three (3) times per day as a rescue medication. Rescue medication will be captured on the study-provisioned smartphone/trial application. **Subjects are not to take rescue medication on clinic visit days, Day 4 (Visit 2) and Day 14 (Visit 3).**

Doses for the Phase 2 study are based on many years of historical use of tolperisone for treatment of painful muscle spasms where the therapeutic dose is generally 300 to 450 mg per day. In addition, the total daily dose of 600 mg was selected to explore a higher dose range to optimize efficacy without impacting safety. A previous clinical study (AV650-018) conducted in subjects with multiple sclerosis-associated spasticity using doses up to 900 mg/day for up to 48 weeks did not show an increase in adverse events.

See Investigator's Brochure for further information.

8. STUDY OBJECTIVES AND ENDPOINTS

8.1. Primary Objective

The primary objective of this study is to assess the efficacy of tolperisone daily doses 150, 300, 450, and 600 mg for relief of pain due to acute back muscle spasm.

8.2. Secondary Objectives

The secondary objectives of this study are:

- To assess the safety and tolerability of tolperisone in subjects with pain due to acute back spasm.
- To determine the onset of action of tolperisone in treatment of pain due to acute back spasm.
- To determine the duration of pain relief of tolperisone in treatment of pain due to acute back spasm.
- To determine the need for rescue medication when treated with various doses of tolperisone for pain due to acute back spasm.

8.3. Primary Endpoint

The primary endpoint for this study is subject-rated pain due to acute back spasm using a Numerical Rating Scale (NRS; 0-10 scale, from no pain to worst possible pain) on Day 14 (“right now” time point).

8.4. Secondary Endpoints

The secondary endpoints for this study include the following. For these endpoints, baseline is defined as the last assessment prior to the first dose of study drug.

Efficacy Endpoints:

- Subject-rated pain due to acute back spasm using an NRS (0-10 scale, from no pain to worst possible pain) on Day 4 “right now”.
- Subject rating of medication helpfulness (SRMH; 1-5 scale, from poor to excellent) on Days 4 and 14.
- Subject-rated NRS (0-10 scale) of pain due to acute back spasm on Days 1 to 14; average over the past 12 hours.
- Subject-rated NRS (0-10 scale) of pain due to acute back spasm on Days 1 to 14; average over the past hour.
- Subject-rated NRS (0-10 scale) of average pain due to acute back spasm on rest or movement, rated at the end of the day on Days 1 to 14.
- Time to relief of pain from baseline due to acute back spasm using subject-rated NRS (0-10 scale) on Days 1 to 14.

- Clinician’s Global Impression of Severity (CGI-S) (1–5 scale) at baseline (Day 1).
- Clinician’s Global Impression of Change (CGI-C) 1-7 scale from worse to marked improvement) on Days 4 and 14.
- Patient’s Global Impression of Severity (PGI-S) (1-5 scale) at baseline (Day 1).
- Patient’s Global Impression of Change (PGI-C) based on subject’s global assessment (1-7 scale, from worse to marked improvement) on Days 4 and 14.
- Functionality assessment: fingers to floor distance (FFD) is an index of mobility of the spinal cord and is measured as distance in cm when standing with the spinal cord flexed with complete extension of knee joint, on Days 4 and 14 compared to baseline (Day 1) (assessments should be conducted at the same time of day for all three time points).
- Disability assessment at baseline (Day 1), Day 4, and Day 14:
 - Oswestry Pain and Disability (ODI) questionnaire (10 questions with one answer each for pain intensity, personal care, lifting, walking, sitting, standing, sleeping, sex life [if applicable], social life, and traveling).
- Use of rescue medications (measured daily, assessed as number of rescue tablets administered by the subject via smartphone/use of trial application). Patients are instructed not to take rescue medications on the day of clinic visits on Day 4 and 14.
- Quality of sleep rated by subjects starting at baseline (Day 1) and on Days 2 to 14.
- Visual Analogue Scale (VAS) score for subject-reported sleepiness measured in the clinic on at Day 4.

Safety Endpoints

- Clinical evaluations include:
 - Vital signs (blood pressure, heart rate, respiratory rate, body temperature)
 - Orthostatic effects on blood pressure
 - Physical examinations
 - 12-lead electrocardiograms (ECGs)
- Laboratory safety tests include blood chemistry, hematology, urinalysis, and urine pregnancy tests for women of childbearing potential
- Adverse events (AEs)

9. SUBJECT DEFINITION

A sufficient number of subjects will be screened to ensure the enrollment of approximately 400 subjects. Individuals are eligible for this study if they meet all inclusion and no exclusion criteria. The criteria below will be assessed at the Screening/Baseline visit.

9.1. Inclusion Criteria

1. Ambulatory male or female, 18 to 65 years of age.
2. Current acute back pain and/or stiffness due to acute and painful muscle spasm starting within 7 days prior to study entry and more than 8 weeks after the last episode of acute back pain.
3. Subjects must have pain of 4 or more on the subject “right now” rating of pain intensity NRS scale of 0 – 10 points at baseline.
4. Must be willing to discontinue all medication used for the treatment of pain or muscle spasm on study entry at Day 1 including but not restricted to:
 - a. Ibuprofen (Motrin)
 - b. Diclofenac (Voltaren)
 - c. Celocoxib (Celebrex)
 - d. Naproxen (Aleve)
 - e. Tolmetin (Tolectin)
 - f. Cyclobenzaprine (Flexeril)
 - g. Cyclobenzaprine (Amrix)
 - h. Metaxolone (Skelaxin)
 - i. Methocarbamol (Robaxin)
 - j. Other nonsteroidal anti-inflammatory drugs (NSAIDs; e.g., aspirin)
 - k. Carisoprodol (Soma)
 - l. Tizanidine (Zanaflex, Sirdalud)
5. Pain localized below the neck and above the inferior gluteal folds.
6. Body mass index ranging between 18 and 35 kg/m².
7. All subjects must be capable of understanding and complying with the protocol and have signed the informed consent document.
8. Female subjects must have a negative urine pregnancy test at screening, must be postmenopausal (amenorrhea for at least 2 years), surgically sterile, or practicing or agree to practice an effective method of birth control if they are sexually active before study entry, during the study and for 2 weeks after the end of the study by using an acceptable method of contraception. Acceptable methods of birth control must be used for at least 14 days prior to the use of study drug. Acceptable methods of birth control include oral, injectable, subdermal implant, vaginal or patch contraceptives, intrauterine device (IUD; copper or hormonal IUD), or double-barrier method (e.g., condom, diaphragm or cervical cap with spermicidal foam, cream, gel, or suppository).
9. Subjects must be willing and able to comply with scheduled visits, treatment plan, laboratory tests, and other study procedures.

9.2. Exclusion Criteria

1. Unwillingness to stop taking pain or antispasmodic medication other than the study medication (specifically opioid use [e.g., Vicodin], barbiturates, and cannabis).
2. Chronic pain for the previous 3 months or longer, on more days than not.
3. Radicular pain in the lower extremity (i.e. pain radiating below the knee), sciatica pain down the leg, or pain below the knee (indicating a lumbar radiculopathy); radicular pain in the upper extremity, radiating into the forearm or hand (indicating a cervical radiculopathy).
4. Concomitant severe pain in a region other than the back.
5. Spinal surgery within 1 year of study entry.
6. Back pain due to major trauma (e.g., motor vehicle accident, fracture of bone) unless resolved for more than 1 year.
7. Treatment of back pain ongoing with non-pharmacological therapy (e.g., acupuncture, chiropractic adjustment, massage, Transcutaneous Electrical Nerve Stimulation [TENS], physiotherapy).
8. Female subjects who are pregnant or lactating.
9. Subjects who are taking Baclofen (Lioresal, Liofen, Gablofen, etc.) or Botox (onabotulinumtoxin A) for pain.
10. Subjects who test positive for alcohol by breathalyzer test.
11. Known history or symptoms suspicious of:
 - a. Spinal fracture within previous 3 years
 - b. Osteoporosis with fracture
 - c. Cancer except cutaneous cancers (e.g., melanoma, squamous cell carcinoma)
 - d. Constitutional symptoms such as recent unexplained chills or weight loss
 - e. Spinal infection
 - f. Intravenous drug abuse
 - g. Immunosuppression
 - h. Cauda equine syndrome
 - i. History of chronic severe scoliosis (childhood)
12. Myasthenia gravis.
13. Recent history of severe hepatic insufficiency, i.e., aspartate aminotransferase (AST)/alanine aminotransferase (ALT) above 3 times the upper limit of normal (ULN).
14. Recent history of severe renal insufficiency, i.e., serum creatinine value above 2.5 mg/dL.
15. History or presence of a severe infection, major surgery or trauma, severe metabolic, endocrine or electrolyte disturbances.
16. A major illness, requiring hospitalization during the 3 months before commencement of the screening period.
17. Inflammatory arthritis, or other diseases known to cause intermittent or chronic pain.

18. Subjects who have had a recent history (less than 2 years before entering the study) of drug or alcohol abuse, or current positive urine drug screen. Alcohol abuse is defined as current consumption of more than three alcoholic beverages per day.
19. History of seizure disorder other than Infantile Febrile Seizures, family history of seizure, or history of head trauma with loss of consciousness.
20. Disability claim for back pain, or pending legal issue regarding back pain.
21. Subjects who have received treatment with an investigational product/device within 30 days prior to study entry.
22. Subjects who have a history of allergic reaction to tolperisone, eperisone, or other skeletal muscle relaxants, lidocaine, acetaminophen or NSAIDs or any components of these study medications.
23. Any other condition that, in the opinion of the Investigator, would adversely affect the subject's ability to complete the study or its measures.
24. Subjects who are unwilling to stop taking moderate to potent inhibitors of cytochrome P450 (CYP) isozymes CYP2D6 and CYP2C19, which are likely to cause drug interactions with tolperisone HCl (e.g., medications such as paroxetine and fluvoxamine).
25. Subjects who are a site staff member, relative, or friend of a site staff member or subjects in same household or who are related to each other.
26. Subjects with clinically significant cardiovascular disorders, such as ischemic heart disease, arrhythmias, poorly controlled hypertension, or history of acute myocardial infarction.
27. Subjects with QT interval greater than 480 milliseconds (msec) or greater than 450 msec if accompanied by a partial bundle branch block, or other clinically significant ECG abnormality at Screening in the judgement of the Investigator.
28. Subjects with diastolic blood pressure less than 50 mmHg or greater than 105 mmHg; sitting heart rate less than 50 beats per minute (bpm) or greater than 110 bpm (after approximately 3 minutes at rest); or heart rate by ECG less than 50 or greater than 110 bpm at Screening.

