10. STUDY DESIGN

10.1. Summary of Study Design

This is a double-blind, randomized, placebo-controlled, parallel group study of the efficacy and safety of multiple doses of tolperisone administered TID in approximately 400 male and female subjects experiencing back pain due to or associated with muscle spasm. The tolperisone groups consist of dose levels of 150, 300, 450, and 600 mg administered TID in doses of 50, 100, 150, or 200 mg for 14 days, with a visit at 28 days as follow-up. Subjects randomized to the placebo group will receive matching placebo tablets TID for 14 days. Subject participation will be approximately 4 weeks.

Subjects will be screened for eligibility for participation in the study at Screening/Baseline Visit 1 (Day 1) after reviewing and signing the informed consent form. Subjects meeting all inclusion/exclusion criteria will then be randomized into the study (Day 1) and begin dosing this same day. If needed, screening assessments may be completed up to 3 days prior to Day 1 (first dose) as described below.

It is highly recommended to complete all screening and baseline assessments on the same day the subject presents at the site due to their acute pain relief needs. However, to accommodate real world logistical issues and time constraints of either the subject or site, the site has the flexibility to allow completion of screening assessments within 3 days (-3 days) prior to Day 1 baseline assessments, deployment of study-provisioned smartphone/download of trial application on subject's smartphone, randomization, and first dose (in that order).

After completing all screening and baseline assessments by/on Day 1, subjects will receive all study drug and rescue medication (acetaminophen 500 mg) and will be instructed to begin taking their study drug that same day. Depending on the time of their clinic visit, they should be instructed to begin dosing with either the midday dose (12-2 pm) or the evening dose (6-8 pm). Subjects will be instructed to continue taking study drug TID through Day 14 and complete dosing diary and daily ePRO assessments.

Subjects will return to the clinic to complete the procedures listed in the Schedule of Procedures on Day 4 (± 1 day; Visit 2) and Day 14 (+1 day, End of Treatment [EOT] visit, Visit 3). Subjects must also return to the clinic for a follow-up visit on Day 28 (+3 days, 2-week follow-up visit, Visit 4).

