11.2.3. Clinic Visit 2: Day 4 (± 1 Day)

On Day 4, subjects return to the clinic to undergo the following assessments:

- Alcohol breathalyzer and urine drug screen. A positive test result for urine drug or alcohol breathalyzer at any time during the study will terminate the subject from further participation in the study.
- Abbreviated physical examination
- Neurological examination
- Vital signs
- Document AEs
- Subject rating of pain (NRS) “right now” via the site study-provisioned tablet
- Subject rating of medication helpfulness via the site study-provisioned tablet
- Global clinical impression of improvement by the physician (CGI-C) via the site study provisioned tablet

- Global impression of improvement by the subject (PGI-C) via the site study-provisioned tablet
- Functionality assessment:
 - Fingers to Floor Distance (FFD)
- VAS via the site study-provisioned tablet
- Disability assessment at Day 4:
 - Oswestry Disability Index (ODI) via the site study provisioned tablet
- For the select group of sites and subjects who will undergo PK assessments, a single blood sample will be drawn on Day 4 after all other assessments have been completed.
- Any changes or additions to prior concurrent medication use will be recorded. Confirm that no rescue medications were taken on Day 4 (Visit 2).
- Site staff to review returned study drug and rescue medication against the eDiary dosing information to evaluate compliance.

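### Exclusion 24 sets no last-use interval for CYP2D6/CYP2C19 inhibitors before a same-day first dose: a minor early safety gap, essentially for CYP2C19 inhibitors at 600 mg/day

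*Protocol*

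**What the plan says.** Exclusion 24, in Protocol Section 9.2 and in the same terms in the Synopsis, removes "Subjects who are unwilling to stop taking moderate to potent inhibitors of cytochrome P450 (CYP) isozymes CYP2D6 and CYP2C19". The criterion names paroxetine and fluvoxamine as examples. Neither the protocol nor the SAP states how long before the first dose such a drug must have been stopped.

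The first dose comes quickly. Section 10.1 states: "Subjects meeting all inclusion/exclusion criteria will then be randomized into the study (Day 1) and begin dosing this same day". It follows at midday or in the evening of Day 1. Screening may be spread over the 3 preceding days, but this is optional, and same-day completion is strongly encouraged because subjects need acute pain relief.

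Section 7.1 gives the size of the interaction. In a Phase 1 study, "the tolperisone plasma exposure increased approximately 2 fold following concomitant administration with paroxetine", a CYP2D6 inhibitor, and it "increased by 3- to 4- fold following concomitant administration with" fluvoxamine, a CYP2C19 inhibitor. The same section reports that "subjects who were classified as CYP2D6 intermediate metabolizers had approximately 50% higher exposure to tolperisone following oral dosing than fast metabolizers", and that bioavailability rose as metabolic activity fell across the four genotypes. No genotype is excluded.

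Section 7.3.2 cites an earlier study in multiple sclerosis spasticity which, "using doses up to 900 mg/day for up to 48 weeks did not show an increase in adverse events".

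**The concern.** A criterion meant to keep strong metabolic inhibition out of the trial tests only the subject's intention. Someone who took fluvoxamine on the morning of Day 1 and agrees to stop meets the rule and takes tolperisone a few hours later. Continuing inhibition during treatment is prevented; inhibition carried into the first doses is not.

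What is at stake is the safety of a few subjects in the first days, mainly at the top dose. After Day 1, ECG and laboratory tests are next scheduled on Day 14, by which time residual inhibition should have faded.

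The eligibility criteria can carry a pre-dose interval where the sponsor wants one. Inclusion 8 states: "Acceptable methods of birth control must be used for at least 14 days prior to the use of study drug". Exclusion 21 sets 30 days for other investigational products. Amendment 1 was written to secure a generally healthy, low-risk population, so a last-use interval would serve an aim the sponsor has already adopted.

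**Working it through.** The plan has no figure of its own to reproduce on this point. The check asks how much residual inhibition would bring exposure above that of 900 mg/day, and how slowly the inhibition would have to fade.

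**Inputs from the protocol.** Exposure factor F on co-administration: 2 (paroxetine), 3 to 4 (fluvoxamine). Intermediate metabolizers: about 1.5. Daily doses: 150, 300, 450 and 600 mg, with 80 subjects per arm. Benchmark: 900 mg/day. Exposure is more than dose-proportional over single doses of 150 to 450 mg; no exponent is given.

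**Assumptions.** Exposure is proportional to dose^b, with b = 1 (proportional) or b = 1.5 (sensitivity value). After stopping on the morning of Day 1, the factor fades as f(t) = 1 + (F − 1) × 0.5^(t/h), with t in days and h the half-life of the inhibitory effect. F is taken as the same at every dose. All inhibitor users start at the full co-administration factor, which is an upper bound.

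**Step 1: factor needed to reach 900 mg/day-equivalent exposure.** Threshold = (900/dose)^b. For 600 mg/day this is 1.5^1 = 1.5, or 1.5^1.5 = 1.84.

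| Arm (mg/day) | b = 1 | b = 1.5 |
|---|---|---|
| 600 | 1.5 | 1.84 |
| 450 | 2.0 | 2.83 |
| 300 | 3.0 | 5.2 |
| 150 | 6.0 | 14.7 |

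Because exposure is more than dose-proportional, the b = 1 column is a lower bound.

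**Step 2: half-life needed to pass the threshold on Day 2** (t = 1, the first full three-times-daily day). The number of half-lives spent above the threshold is k = log2[(F − 1)/(threshold − 1)], so Day 2 needs h > 1/k days. Worked case, 600 mg/day, F = 3, b = 1.5: k = log2(2/0.837) = 1.26, so h > 0.80. For F = 4: k = log2(3/0.837) = 1.84, so h > 0.54.

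| Arm, F | h (days), b = 1 | h (days), b = 1.5 |
|---|---|---|
| 600, 2-fold | > 1.0 | > 3.9 |
| 600, 3-fold | > 0.50 | > 0.80 |
| 600, 4-fold | > 0.39 | > 0.54 |
| 450, 2-fold | never | never |
| 450, 3-fold | > 1.0 | > 7.7 |
| 450, 4-fold | > 0.63 | > 1.40 |
| 300, 4-fold | > 1.7 | never |

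The remaining 300 mg/day cases (2- and 3-fold) and every 150 mg/day case never pass.

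**Step 3: time above the threshold in the 600 mg/day arm**, equal to k × h, for an assumed h of 0.5 to 2 days:

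- From 3-fold: 1.0–4.0 days at b = 1; 0.6–2.5 days at b = 1.5.
- From 4-fold: 1.3–5.2 days at b = 1; 0.9–3.7 days at b = 1.5.
- From 2-fold: 0.5–2.0 days at b = 1; 0.1–0.5 day at b = 1.5.

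**Step 4: what the design already accepts.** An intermediate metabolizer in the 600 mg/day arm has about 600 × 1.5 = 900 mg/day-equivalent exposure under proportional scaling, for all 14 days. Slow metabolizers have more. A fading 2-fold CYP2D6 effect exceeds 1.5 for only one half-life (log2[(2 − 1)/(1.5 − 1)] = 1), so it adds little.

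**Step 5: Day 14.** With t = 13, F = 4 and h = 2, the residual factor is 1 + 3 × 0.5^6.5 = 1.03.

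**Step 6: subjects.** The documents give no prevalence. At an assumed 1–5%, the count is 0.8–4 of the 80 subjects at 600 mg/day. That covers users of any of these inhibitors; users of CYP2C19 inhibitors are only part of it.

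**The case against.** The strongest reply is that this is a reasoned trade-off. Stopping at entry is the form the protocol uses for other medicines (inclusion 4, exclusion 1), and same-day dosing has a stated clinical reason. There are also partial controls. Section 14 bans psychoactive medicines during participation and has the investigator review routine medication, and exclusion 23 leaves room for judgement. The Synopsis counts Screening as part of participation, so the ban could reasonably cover both named inhibitors before the first dose. Day 4 brings adverse event review, vital signs, physical and neurological examinations and the sleepiness scale ("VAS via the site study-provisioned tablet").

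Much of this stands, and it keeps the point minor. It does not close the gap. With same-day screening the ban reaches back only hours, and at most 3 days; it does not cover inhibitors that are not psychoactive; and neither investigator review nor exclusion 23 states a CYP rule or interval. The need for quick relief explains the urgency but does not address carry-over.

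Two further replies also stand. Proportional scaling overstates the effect, because exposure is more than dose-proportional: at b = 1.5 the 300 mg/day arm drops out and the 2-fold case nearly does. The interaction study itself is human experience under inhibition: across the healthy-volunteer studies no adverse event other than headache exceeded 5% of subjects. Since Section 7.1 does not give the dose in that study, this does not establish safety at 600 mg/day.

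A reader might multiply 600 by 3 to 4 and infer exposure equivalent to 1800–2400 mg/day. The documents do not support that. The factors describe continued co-administration, these subjects have stopped, and at b = 1.5 even full inhibition gives 1248–1512.

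**Conclusion.** The point holds as a minor early safety gap. Exclusion 24 does not prevent, at the first dose, the interaction it is written to prevent. The gap is essentially confined to CYP2C19 inhibitors in the 600 mg/day arm. The 450 mg/day arm is a less robust case: at b = 1.5 it needs an offset half-life above 1.4 days from 4-fold, or 7.7 days from 3-fold. Residual CYP2D6 inhibition is close to what the design already accepts.

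The size rests on assumed values for the dose exponent, the exponential offset and its half-life, and the prevalence of recent use.

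Three stronger readings are not supported:

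- **That subjects would pass a safety limit.** The 900 mg/day figure is the highest experience cited, in a different patient group, and no toxicity threshold is given. Passing it means exposure beyond that experience, not shown harm.
- **That the primary result is biased.** At the slowest offset considered the factor on Day 14 is about 1.03.
- **That a 14-day washout is required.** No washout length can be derived from the documents.

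**What to change.** Reword exclusion 24 in Section 9.2 and the Synopsis along these lines: *Use of a moderate to potent inhibitor of CYP2D6 or CYP2C19 within a sponsor-set interval before first dose (e.g., 14 days, or 5 half-lives of the inhibitor if longer), or unwillingness to avoid them through Day 14.* Add these inhibitors to Section 14 as prohibited through Day 14.

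The interval is a clinical-pharmacology judgement for the sponsor. As a guide, five half-lives of the inhibitory effect leave a factor of 1 + 1/32 = 1.03 from 2-fold, or 1 + 3/32 = 1.09 from 4-fold. Fourteen days covers effect half-lives up to 14/5 = 2.8 days. The half-life of the effect need not equal that of the drug.

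No new data or SAP output is needed. Breaches become eligibility deviations, handled by the existing deviation review (SAP 7.3.2) and per-protocol sensitivity analysis (SAP 7.4.6.6).

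The cost is recruitment. Recent users are in effect screened out, since pain must have started within 7 days of entry and the 3-day screening window covers five half-lives only up to 3/5 = 0.6 day. At the assumed 1–5% prevalence, about 4–20 of 400 subjects would have to be replaced by further screening. This is a cheap improvement.
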